6.10 Description and Instruction for Case Report Forms, Assessments and Procedures

6.10.1 Informed Consent

The ICF will, in writing understandable to the subject, describe the study and its purpose. It will outline the potential benefits and the potential risks as well as what alternative procedures may be available. The confidentiality of the subject's participation will be confirmed and the confidentiality of the subject's data and the study data will be described. Compensation and any anticipated expenses will be disclosed. Subject will be informed that any new findings which may affect their participation will be disclosed. As applicable circumstances under which the investigator or the sponsor may terminate the study will be explained.

6.10.2 Inclusion / Exclusion Criteria CRF

This form lists all of the criteria the subject must meet to be eligible for the study. ALL inclusion criteria must be met and NO exclusion criteria can be present for a subject to be eligible for the study.

6.10.3 Demographics, Medical Conditions and Medical Co-morbidities CRF

This will document subject's demographics including but not limited to, date of birth, gender, height, weight, BMI, ethnicity, current tobacco use and current alcohol use.

Current medical conditions and parameters, especially relative to inclusion and exclusion criteria, will be documented. This may include but is not limited to, HbA1c level, Ankle-Brachial Test, transcutaneous oxygen pressure test, (TcPO₂), toe pressure test, and Monofilament Test.

History and current conditions of the DFU will be documented including but not limited to duration of ulcer, maximum height, length and depth, number of previous attempts to close with a biological solution and biological wound treatments previously used.

The subject's medical co-morbidities and history will document major system concomitant pathologies, drug allergies and current medication use.

6.10.4 Wound Assessment and Treatment CRF

This will document whether the wound is closed. To be closed there must be 100% epithelialization of the wound, no discernable exudate, and no further need for dressing.

Wound area and volume will be assessed by gross measurement of length, width and depth and assessed for infection.

With initial application during the treatment visit, and then when clinically indicated additional applications of MIROMESH will be documented including lot number, type, and size of MIRODERM Biologic Wound Matrix.

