
Study Design and Procedures
	
This is a multi-center post-market, single-arm, prospective follow-up study
 
Assessment and Roll-in Phase
 
Subjects will be recruited by the treating physicians, screened for eligibility, invited to participate in the study and provide informed consent. The subject's demographics, medical history, co-morbidities and wound characteristics will be documented and the subject will complete a SF-36 quality of life questionnaire. Subject will be instructed on proper nutrition.
 
Wound will undergo sharp debridement, be traced, photographed, and dressed per standard of care. Two tissue sections of at least 2mm will be retained for histological analysis. Subject will be fitted with and instructed on an offloading device. Subjects will return for MIRODERM treatment in two weeks.
 
Treatment Phase
 
On treatment day, wound will undergo sharp debridement, be traced, photographed and MIRODERM Biologic Wound Matrix will be applied. After treatment, subjects will be considered enrolled into the trial. Details of treatment will be documented.
 
Subject will present weekly for the next twelve weeks. The dressing will be changed and may undergo further MIRODERM treatment if indicated. The wound will be traced and photographed. Physician will document their assessment on whether the wound is 100% closed.
 
Subjects whose wound is completely closed at or prior to 12-weeks post-treatment, will be instructed to return 1-week following for a confirmation visit. Subjects whose wound is not assessed as closed by 12-weeks post-treatment, will have two tissue sections of at least 2mm collected, complete a quality of life assessment, and will then be discontinued per protocol.
 
Confirmation Phase
 
Subject will complete a quality of life assessment and have their wound area photographed. Physician will confirm the wound is still closed and the subject will be discontinued per protocol. If wound has reopened subject will return to the treatment phase.

Subject Participation
	
Subjects can be expected to reasonably participate in the study for a minimum of 9 weeks and a maximum of 15 weeks depending treatment course.

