
Schedule of Visits
	
 1 Assessment and Roll-in (2-weeks prior to procedure) 2 Index Procedure 3 1-Week post-procedure (\pm 2 days) 4 2-Week post-procedure (\pm 2 days) 5 3-Week post-procedure (\pm 2 days) 6 4-Week post-procedure (\pm 2 days) 7 5-Week post-procedure (\pm 2 days) 8 6-Week post-procedure (\pm 2 days) 9 7-Week post-procedure (\pm 2 days) 10 8-Week post-procedure (\pm 2 days) 11 9-Week post-procedure (\pm 2 days) 12 10-Week post-procedure (\pm 2 days) 13 11-Week post-procedure (\pm 2 days)

	
14 12-Week post-procedure (\pm 2 days)
 
15 Confirmation: 13-Week post-procedure (\pm 2 days)
 
All subjects will be offered a \$25 gift card for completing weekly follow-up during the treatment phase.

Study Duration	1 Year
Assessment Tools	
Ankle Brachial Index
 
HbA1c
 
Monofilament test for neuropathy
 
Photograph
 
E-Z Graph Wound Assessment System
 
Sf-36v2 Health Survey

Primary Endpoint	Proportion of subjects who have a closed wound at or before 12 weeks after the index procedure.
Primary Hypothesis	
As an observational study, there is no formal hypothesis test. The precision of the estimate of the proportion of subjects who successfully close will be determined.
 
Assumptions:
 
 • A minimum 50 subjects • A 95% Confidence Interval of the estimate • A 2-sided confidence interval • Using exact Clopper-Pearson estimation 
The Confidence Intervals (CI) at selected success rates are as follows:
 
 • @ 25%; CI = 25.4% Boundaries 13.8%-39.3% • @ 50%; CI = 28.9% Boundaries 35.5%-64.5% • @ 75%; CI = 25.4% Boundaries 60.7%-86.2% 
Thus, a sample size of 50 should allow for a reasonable estimate of treatment success at 12 weeks and for reasonable comparisons to historical controls.

Statistical Analysis	
Descriptive statistics including but not limited to mean, standard deviation, frequency and percentages will be used to describe demographics, medical history, and characterize baseline variable as appropriate.
 
A Z-test will be used to assess whether the proportion of subjects that were successful is greater than zero. Kaplan-Meier analysis will be used describe the survival curve assuming complete closure as the event of interest. A repeated measure ANOVA will be used to assess changes in, wound area and quality of life over time.

TABLE OF CONTENTS

1	Background	13

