5.3 Potential Benefits of the Procedure

The potential benefit of treatment with MIRODERM Biologic Wound Matrix is closure of the refractory DFU and a reduction in the probability of infection, increased wound area and eventually amputation of the affected limb.

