6.6.4 Wound treatment – MIRODERM application and dressing

MIRODERM Biological Wound Matrix will be applied consistent with the IFU and wound will be dressed. An appropriate size of MIRODERM will be placed over the wound and, as needed, bolstered such that MIRODERM comes into contact with the maximum amount of wound surface. MIRODERM should be secured with Steri-strips, sutures or staples. Primary dressing shall have a non-adherent wound contact layer. Secondary dressing shall be roll gauze. No other biological material shall be used. ***Subjects will be considered enrolled into the study subsequent to treatment with MIRODERM Biologic Wound Matrix.*** Treatment details will be recorded.

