6.9 Study Exit

Subjects will be discontinued from the study per protocol. Under the following circumstances:

- Subject's index wound has been determined to be fully closed and remains closed at their 1-week follow-up confirmation
- Subject had completed their 12-week post-treatment follow-up and their index wound has not completely healed
- Subject presents with osteomyelitis of the study DFU or an infection of the study DFU
- Subject voluntarily withdraws consent.
- Subject lost-to-follow-up
- Subject death

When a subject is study exited, patients are no longer considered participants in the study and have no further obligations under the protocol. patients may undergo continued care as deemed appropriate by physician of record.

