6.10.8 Protocol Deviation CRF

This form will document the deviations from the study protocol. As needed it will document immediate corrections or corrective actions.

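### The closure endpoint has no rule for an ulcer that is grafted, surgically closed, treated with another biologic or amputated before Week 12, so any resulting error raises the closure rate

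*Combined protocol and SAP*

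**What the plan says.** The synopsis gives the primary endpoint as "Proportion of subjects who have a closed wound at or before 12 weeks after the index procedure", and section 4.2 says the same in substance. The objective in section 4.1 is narrower: it concerns the effectiveness of MIRODERM in closing these ulcers.

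Closure is defined once, in section 6.10.4: "To be closed there must be 100% epithelialization of the wound, no discernable exudate, and no further need for dressing". The treating physician makes the judgement (synopsis: "Physician will document their assessment on whether the wound is 100% closed"). A visit one week later checks whether the wound is still closed, and section 6.9 makes this an exit condition: "Subject's index wound has been determined to be fully closed and remains closed at their 1-week follow-up confirmation".

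The other exits in section 6.9 are 12 weeks completed without healing ("Subject had completed their 12-week post-treatment follow-up and their index wound has not completely healed"), infection or osteomyelitis of the study ulcer, withdrawal of consent, loss to follow-up and death. Section 6.2 lists the same four reasons for leaving early.

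Section 6.6.4 rules out competing products: "No other biological material shall be used". Section 6.7.3 carries this into follow-up by requiring reapplication to be consistent with 6.6.4. Breaches are recorded under 6.10.8 ("This form will document the deviations from the study protocol"). Section 11 adds prior sponsor authorization, an explanation, reporting in some cases, and corrective action where appropriate.

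Section 7 defines no analysis population and no handling of events that interrupt or replace treatment. Its one relevant rule is that missing values are ignored and the available n is used.

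**The concern.** The closure rate is meant to describe what MIRODERM does, but the definition can be met by a wound that something else closed. A subject whose ulcer is grafted, surgically closed or switched to another biologic has not been healed by the study device alone. In a single-arm effectiveness study such a subject is conventionally a non-responder. Amputation is clearer still as an outcome, since section 5.3 names as a hoped-for benefit "a reduction in the probability of infection, increased wound area and eventually amputation of the affected limb".

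The events are plausible. Eligible ulcers have been open for at least 90 days and have failed at least two treatments with a biologic (6.5.2).

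The study has no control arm in which the same error could offset itself. The synopsis and section 7 intend the rate for comparison with historical controls, the literature and a history of not healing. The sponsor analyses the data itself (section 18) and may do so intermittently (section 7). Without a rule set in advance, these cases would be classified one by one after the results are known.

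**Working it through.** **1. Follow each event through the text.**

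| Event after first MIRODERM application | Exit under 6.2 or 6.9? | Score under 6.10.4 | Handling in section 7 |
|---|---|---|---|
| Skin graft or surgical closure, then epithelialised and dry | No | Meets the definition | Counts as success |
| Another biologic, then epithelialised and dry | No (deviation only) | Meets the definition | Counts as success |
| Amputation of the part bearing the ulcer | No, unless infection or osteomyelitis came first | Not settled: success, failure or missing | If missing, ignored |

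A miscounted success raises the numerator. A dropped failure lowers the denominator. Scoring an amputation as a failure causes no error. No path lowers the rate. In the Kaplan-Meier analysis named in the synopsis, censoring at the event date would treat the subject as still able to heal.

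**2. Reproduce the plan's interval.** Inputs from section 7: n = 50, two-sided 95%, exact Clopper-Pearson. With x closures, lower = Beta quantile(0.025; x, n − x + 1) and upper = Beta quantile(0.975; x + 1, n − x). For x = 25 this gives 35.53% to 64.47%, width 28.95 points, which agrees with the plan's 35.5%–64.5%.

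**3. Cases miscounted as closed.** The number k is an assumption, because the documents give no rate. Each case moves the rate by 1/50 = 2.0 points, or 1/65 = 1.5 points at the maximum enrolment. If 25 of 50 are recorded as closed:

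| k | Corrected rate | 95% interval |
|---|---|---|
| 0 | 25/50 = 50% | 35.5–64.5 |
| 1 | 24/50 = 48% | 33.7–62.6 |
| 2 | 23/50 = 46% | 31.8–60.7 |
| 3 | 22/50 = 44% | 30.0–58.7 |

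The shift in points is the same at other rates. With k = 3, 13/50 = 26.0% (14.6–40.3) becomes 10/50 = 20.0% (10.0–33.7), and 38/50 = 76.0% (61.8–86.9) becomes 35/50 = 70.0% (55.4–82.1).

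**4. Failures dropped as missing.** Here the numerator stays at 25 and the denominator shrinks. One dropped gives 25/49 = 51.0%, and three dropped gives 25/47 = 53.2%, against 50.0% with all 50 kept. That is about 1 point per subject, half the effect of a miscounted success.

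**The case against.** A reader might infer that an amputated ulcer will be scored as a success. The documents do not support that. Section 6.10.4 requires the wound itself to be fully epithelialised, and a removed ulcer does not plainly satisfy this. Its score is open, and the dropped-as-missing path has the smaller effect shown in the working. That path is also an instance of section 7's general missing-data rule.

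A reader might also infer that closure rests on appearance alone, or that the form obliges the physician to record closure. Both go too far. Whether a dressing is still needed is a clinical judgement, closure is rechecked after a week, and the sample forms in Appendix B are not in the text available. But neither the judgement nor the recheck asks how the wound closed.

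Nor is a deviation form the only consequence of using another biologic, since section 11 goes further. What is missing is a consequence for the analysis.

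Some cases will be removed or visible by other routes. Infection and osteomyelitis lead to exit, a patient seeking other treatment may withdraw, and adverse events definitely or likely related to the study wound or treatment are recorded with their treatment (14.2, 14.3). These routes help to identify cases but do not set their endpoint status.

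Finally, the likely effect is small against an interval about 29 points wide, and the primary endpoint carries no formal hypothesis. This limits the weight of the point. It does not remove a bias that runs in one direction and that a larger sample would not cure.

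**Conclusion.** The point holds. As written, a study ulcer that is grafted, surgically closed or given another biologic, and then epithelialises, counts as a MIRODERM success. An amputated ulcer has no settled classification and may drop out of the denominator. Any resulting error in the closure rate is upward.

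At n=50 the size is 2.0 points for each case miscounted as closed and about 1 point for each failure dropped. One to three miscounted cases would put a reported 50% at 48% to 44%. These counts are an assumption, and the true number is probably small because some amputations would follow an infection or osteomyelitis exit. The plan's stated intervals are not in dispute, and the planned sample size is unaffected. The change should be made, but it does not threaten the study.

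**What to change.** Add to section 4.2 and section 7, with a cross-reference in 6.10.4:

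> A subject whose study ulcer, after the first MIRODERM application and by Week 12, is removed by amputation, surgically closed or skin-grafted, or treated with another biologic counts as not closed in the primary proportion, stays in the denominator, and is carried as not closed through Week 12 in the Kaplan-Meier analysis. Sutures or staples used to secure MIRODERM under 6.6.4 are not surgical closure.

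The last sentence is needed because 6.6.4 permits sutures and staples for fixing the matrix. Record the event and its date on the existing Wound Assessment and Treatment CRF. Report a sensitivity analysis that counts these wounds as observed, so that the effect of the rule can be seen.

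This changes classification only. The exit list in 6.9 and the care of subjects stay as they are. The cost is a short passage in two sections, one cross-reference, a dated entry on one form and one extra analysis. The reported closure rate may be slightly lower.

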6.10.5 SF-36v2® Health Survey CRF

The SF-36 is a validated instrument which assesses an individual's current health status and health related quality of life and can be used in health economic analysis. The SF-36 assess 8 sub-scales, vitality, physical functioning, bodily pain, general health perceptions, physical role functioning, emotional role functioning, social role functioning, and mental health. The subscales may also be summarized in two measures assessing physical health and mental health. The SF-36 may be administered as a written survey or verbally.

6.10.6 Study Discontinuation CRF

This form will document when and the conditions under which a subject is exited from the study.

6.10.7 Adverse Event CRF

AE forms will document a description of the AE, onset and resolution dates, treatment, and investigator's assessment of severity and relatedness to the device.

6.10.8 Protocol Deviation CRF

This form will document the deviations from the study protocol. As needed it will document immediate corrections or corrective actions.

6.10.9 Ankle-Brachial Index

The ankle-brachial index is a noninvasive test of peripheral artery disease and an indicator of poor peripheral circulation. The ankle-brachial index test compares a person's blood pressure measured at the ankle with blood pressure measured at the arm. A low ankle-brachial index number can indicate circulatory problems. The ankle-brachial index should be determined at the time of initial assessment if there is no documentation within the past 90 days.

6.10.10 Hemoglobin A1C Test (HbA1C)

The HbA1C test measures the amount of glucose bound to hemoglobin in a red blood cell and is an indicator of blood glucose control over the previous two to three months. This test is used a screening test for diabetes. Values of less than 5.7% are normal, values of 5.75-6.4% are considered pre-diabetic and values of 6.5% or greater are considered diabetic. To be used as the inclusion criteria for this study, potential subjects should, within 90 days of Assessment and Roll-In, have a documented HbA1C value of 12% or less.

6.10.11 Transcutaneous Oxygen Pressure Test (TcPO2)

A TcPO2 test is a non-invasive test to quantify skin oxygenation and is indicative of cutaneous ischemia. TcPO2 levels above 30 mmHg are predictive for spontaneous healing while values of 10 mmHg or less are predictive of an unfavorable course of healing. To be used as the inclusion criteria for this study, potential subjects should, within 90 days of Assessment and Roll-In, have a documented TcPO2 value equal or greater than 30 mmHg.

6.10.12 Toe Pressure Test

A toe pressure test is a vascular test to confirm peripheral artery disease and limb ischemia. A toe pressure cuff is inflated above systolic artery pressure to occlude the vessels. The cuff is slowly deflated to reduce pressure. When blood returns to the vessels the pressure indicated is the toe pressure. To be used as the inclusion criteria for this study, potential subjects should, within 90 days of Assessment and Roll-In, have a documented toe pressure test value equal or greater than 50 mmHg.

6.10.13 Monofilament Test

A monofilament test is a non-invasive method to assess loss of protective sensation by determining if a person can detect pressure on their feet. Generally, a nylon monofilament which may be deformed at a pressure of 10 grams is pressed in an uneven cadence unsystematically upon 10 spots on an individual's foot. The individual is asked to signal when they feel pressure. The inability to detect pressure on 3 or more of the 10 tests will be considered to be positive for peripheral neuropathy. To be used as evidence for peripheral neuropathy, potential subjects should, within 90 days of Assessment and Roll-In, have a documented positive monofilament test.

6.10.14 Wagner Classification

The wound will be classified according to the Wagner Classification System as follows:

Table 2. Wagner's classification for foot ulcers (6)

Grade	Description
Grade 0	Pre- or post-ulcerative site
Grade 1	Superficial ulcer
Grade 2	Penetration into tendon or joint capsule
Grade 3	Involvement of deeper tissues, infection present
Grade 4	Gangrene of the forefoot
Grade 5	Gangrene involving more than two-thirds of the foot

6.10.15 Wound Tissue Sample

During initial debridement and with subjects whose wounds do not close after 12 weeks of follow-up, two tissue sections of at least 2mm from the wound area will be obtained. Each tissue sample will be placed into formaldehyde filled 5 ml plastic sample tubes provided. Using a standard "Sharpie" marker, each tube shall be labeled with subject number and date acquired. Tubes will be stored at room temperature until collected by the sponsor.

6.10.16 Wound width, length and depth assessment

Wound width and height should be measured to the nearest mm using disposable paper ruler. Wound depth should be measured at the maximum depth with reference to the plane of the skin's surface using a sterile cotton tipped applicator and measuring to the plane of the skin's surface.

6.10.17 E-Z Graph Wound Assessment System

This system will be used to assess inclusion exclusion criteria and to document changes in wound size over time. For the purposes of this study, the E-Z Graph® Wound Assessment Worksheet shall be considered a case report form.

Wound surface area measurement will be obtained via tracing using the E-Z Graph® Wound Assessment System. Whenever possible, tracings should be performed by a single person at the study site. The person(s) performing the tracing must be identified on the Delegation of Authority as having responsibility for this task. Measurement for study inclusion will be taken at the Assessment and Roll-in

Visit post-debridement and assessed by the investigator (or trained delegate). Further tracings will be completed at the Treatment Visit and again at each Follow-up Visit post debridement (where applicable). Trace the wound margin from the full-thickness, sharply debrided margins, eliminating any partial thickness involvement.

Tracing measurements will be performed as described below. Care will be taken not to lean heavily on the border or move the transparency while tracing.

1. Complete the information on the top of the E-Z Graph transparency entering the subject ID where Name is indicated and the Date. "Wound Location" and "TX Being Used" do not have to be completed.
2. Enter assessor's name on the appropriate line at the bottom of the text area and above the tracing graph.
3. Lay the E-Z Graph transparency on top of the wound with the center dot of the graph in the middle of the wound and the subject's head at the 12 o'clock position.
4. Use a fine-tipped permanent marker to draw around the full-thickness wound outline. Blue or black are the preferred marker colors for tracing. Trace only the open area of the wound.
5. Bend the lower right corner of the graph to peel off the backing, then align and adhere the graph to the E-Z Graph® Wound Assessment Worksheet. Use care as static electricity may suck graph to paper prematurely.
6. For assessing inclusion criteria, measure the surface area by counting each + symbol that lies mostly within the traced margin. If the center of the + symbol lies outside or directly beneath the outlined margin, do not count it. The number of squares counted will be the wound size in cm² and should be documented in the appropriate area of the Inclusion Exclusion CRF.
7. Make a photocopy of the completed E-Z Graph® Wound Assessment Worksheet and retain it in the subject's medical record. The original E-Z Graph® Wound Assessment Worksheet shall be placed in the E-Z Graph binder for collection and analysis by the sponsor.

In addition to the wound tracing, complete other information on the E-Z Graph Wound Assessment Worksheet as follows:

- STAGE
- WD BASE
- DRAINAGE AMT
- DRAINAGE TYPE
- PERIWOUND
- Yes-No determination
 - ODOR
 - ESCHAR/SLOUGH
 - UNDERMINING
 - TUNNELING

Note: completion of Length, Width and Depth are not necessary as these values are collected on the wound assessment CRF. The back of the E-Z Graph® Wound Assessment Worksheet does NOT need to be completed.

